Note: CHG is the change from baseline to Week 13 in RBANS-DMI.

Combine the analysis results into a single estimation with standard error

```
proc mianalyze parms=lsmeans;
  modeleffects trt01pn;
  ods output ParameterEstimates=lsm;
  by trt01pn;
run;
```

Sample SAS code presented above is for illustrative purposes, and the actual code may be adjusted as needed. Note that all imputed values will be 'forced' to fall into the range of 'possible' values for the RBANS-DMI (which ranges from 40 to 160).

8.1.2. Additional Sensitivity Analysis for the Primary Efficacy Endpoint

In addition, pooling of the two active BPN14770 arms will be performed and a comparison to the placebo arm will be performed, using similar MMRM models as for the primary assessment, for the mITT population.

The primary efficacy population will be the mITT population. The PP population and the CP population outcomes will be used to evaluate the robustness of the mITT results, using the models described above.

A separate sensitivity analysis using a non-parametric (distribution-free) Wilcoxon Rank Sum Test of the pairwise treatment differences will be run for the Week 13 change from baseline data. SAS code similar to the below will be used. A test of the normality of the residuals will be performed to assess the validity of the non-parametric vs parametric assumptions. The results will be presented in a summary table with standard summary statistics as well as the Wilcoxon rank sum means, active vs. placebo rank-sum mean differences and p-values.

```
Proc nparlway data=dat;
  Class treat;
  Var change;
  ods select WilcoxonScores;
Run;
```

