3.4. Determination of Sample Size

The BPN14770-CNS-201 study will enroll 255 subjects (85 per treatment arm), in anticipation of evaluating at least 240 subjects (80 per treatment). The Primary Efficacy Outcome measure will be change from baseline at Week 13 for the Repeatable Battery for the Assessment of Neurological Status - Delayed Memory Index (RBANS DMI).

The normalized mean of the RBANS DMI is 100, with an SD of 15, and the test-retest reliability is 0.80 with no practice effects using alternate versions of the test [Randolph 1998]. RBANS DMI was used in a recent natural history study of Mild Cognitive Impairment (MCI) due to probable AD [Karantzoulis 2013]. In the large amnesic MCI sample (81 subjects), the mean was 73.4 with a SD of 16.5 in a normal distribution. Performance of healthy, age-matched controls was a mean of 101.4 with a SD of 14.4 (81 subjects) yielding estimates of the standard deviation for the DMI from 14.4-16.5. Therefore, the power analysis is based on the assumption that the standard deviation of the response variable is 16.

The power of the proposed study is driven by the assumed difference between BPN14770 25mg (higher dose) and placebo. Based on randomization of 80 subjects per group into the parallel-design study, the probability is 80 percent that the study will detect a treatment difference at a two-sided 0.05 significance level, if the true difference between BPN14770 25 mg and placebo is 7.15 units. Using the standardized mean difference (SMD) to estimate effect size [Faraone 2008], a change of 7.15 units on the DMI score is an effect size of 0.45.

Table 1 provides sample size estimates for 80 percent and 90 percent probability that the study will detect a treatment difference at a two-sided 0.05 significance level assuming the standard deviation of the DMI is 16.

Table 1 Clinical Sample Size (1:1 Active + Placebo) Based on Effect Size (Change From Baseline) And Desired Power

	Number of Subjects Per Group Based on Desired Effect Size (SMD)					
Standardized Mean Difference (SMD)	0.3	0.35	0.4	0.45	0.5	0.75
RBANS DMI change (M1-M2)	4.8	5.6	6.4	7.2	8	12
Number of Subjects (Power 0.8)	176	130	100	79	64	29
Number of Subjects (Power 0.9)	235	173	133	105	86	39

For comparison, a donepezil study reported by Seltzer et al., 2004, randomized a total of 153 subjects (2:1 active vs placebo) and reported treatment benefit at a significance level of 0.03 after 12 weeks of

This document is confidential.

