8.1. Primary Efficacy Endpoint and Analysis – RBANS DMI

The Repeatable Battery for the Assessment of Neurological Status (RBANS) [Randolph 1998] is a brief, individually administered test measuring attention, language, visuospatial/constructional abilities, and immediate and delayed memory. It consists of 12 subtests, which yield five Index scores and a Total Scale score.

Total scores are calculated by adding up the scores for each of the 12 individual subtests and ranges between 0 and 311, where a low score indicates greater impairment. The range of possible scores for the RBANS DMI is 40 to 160.

The primary efficacy outcome measure is the change from baseline to Week 13 in the delayed memory index of the RBANS [Repeatable Battery for the Assessment of Neurological Status - Delayed Memory Index (RBANS DMI)]. Observed cases data (with no imputation for missing values) will be used for primary efficacy analysis.

The original RBANS DMI score and change from baseline will be summarized by treatment group at each time point.

The primary method of analysis will be an MMRM with restricted maximum likelihood estimation, an unstructured covariance matrix, and the Kenward-Roger approximation for denominator degrees of freedom. The model will include fixed effects for treatment, visit (time), the treatment-by-time interaction, ApoE4, pooled study site, the baseline RBANS DMI score as covariate, and a random effect for subject. [Similar models will be defined for the other continuous secondary efficacy endpoints.] Primary inferences will be drawn from treatment differences in the LSmean changes from baseline derived from the MMRM models at Week 13. As additional supportive information, treatment differences for Weeks 1, 4, and 8 will also be derived using the MMRM model. Least Squares Means for each visit and the SE of the LSMeans will be displayed graphically.

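### The Wilcoxon check on the primary endpoint drops the baseline and ApoE4 adjustment, so disagreement with the MMRM could not be attributed to non-normality alone (low severity, nearly free to improve)

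*SAP*

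**What the plan says.** SAP 8.1 bases primary inference on the Week 13 contrast from an MMRM. Its fixed effects, besides treatment, visit and their interaction, include "ApoE4, pooled study site, the baseline RBANS DMI score as covariate". The ANCOVA run on the multiply imputed data (SAP 8.1.1) keeps baseline DMI, ApoE4 and pooled site.

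SAP 8.1.2 then adds a rank-based check of the same endpoint: "A separate sensitivity analysis using a non-parametric (distribution-free) Wilcoxon Rank Sum Test of the pairwise treatment differences will be run" on Week 13 change from baseline. Beside it stands: "A test of the normality of the residuals will be performed to assess the validity of the non-parametric vs parametric assumptions". The sample PROC NPAR1WAY code names treatment as the class variable and change as the analysis variable. It has no STRATA statement, no covariate and no restriction to two arms. The text promises active-versus-placebo p-values from code similar to what is printed.

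Randomization is stratified by ApoE4 (SAP 3.5). The SAP stratifies its CMH row mean scores test for CGI-I by ApoE (SAP 8.2.5) but does not stratify this test.

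**The concern.** A non-parametric check is most informative when it changes the distributional assumption and little else. This one also drops the baseline covariate, ApoE4, pooled site and the information from earlier visits. If the MMRM is significant and the Wilcoxon test is not, there are several possible explanations, and lost precision is among the likeliest. A reader could then take a sound result to be fragile although the data are normal. The study is meant to inform dose selection for Phase 3 (SAP 3.1 and 8.3), so supportive analyses of this kind will be read.

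There is also a practical gap. The printed code makes one run over all treatment levels and selects only the rank-score table. As it stands it does not produce the pairwise p-values that the text promises.

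**Working it through.** **Inputs from SAP 3.4.** 80 per group; "treatment difference at a two-sided 0.05 significance level"; difference 7.15 ("if the true difference between BPN14770 25 mg and placebo is 7.15 units"); SD 16 ("the power analysis is based on the assumption that the standard deviation of the response variable is 16"). The only correlation-type figure is a normative one: "the test-retest reliability is 0.80 with no practice effects using alternate versions of the test".

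**Assumptions.** The correlation r between baseline and Week 13 DMI in this trial is not given. I use 0.5 to 0.8, because restricting entry on DMI may bring it below 0.80. In the simulations 60% of subjects carry ApoE4. Neither document states a power for the Wilcoxon test.

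**Step 1: reproduce the SAP's figure.** 7.15 / (16 × √(2/80)) = 7.15 / 2.530 = 2.826. Power = Φ(2.826 − 1.960) = Φ(0.866) = 80.7%. The noncentral t gives 80.2%. The stated 80% reproduces.

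**Step 2: the planned Wilcoxon test, 16 as the SD of change.** Its asymptotic relative efficiency under normality is 3/π = 0.955. 2.826 × √0.955 = 2.762, so power = Φ(0.802) = 78.9%.

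**Step 3: add baseline adjustment.** With equal variances at the two visits, raw change has variance 2σ²(1 − r) and the adjusted analysis σ²(1 − r²). The ratio of adjusted to raw is (1 + r)/2: 0.90 at r = 0.8 and 0.75 at r = 0.5.

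| r | Wilcoxon | Rank ANCOVA (approx.) | Parametric ANCOVA |
|---|---|---|---|
| 0.8 | 78.9% | Φ(2.762/√0.90 − 1.960) = 82.9% | Φ(2.826/√0.90 − 1.960) = 84.6% |
| 0.5 | 78.9% | Φ(2.762/√0.75 − 1.960) = 89.1% | Φ(2.826/√0.75 − 1.960) = 90.4% |

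The Wilcoxon test trails the rank ANCOVA by 4.0 and 10.2 points. The further gap to parametric ANCOVA (1.7 and 1.3 points) is the ordinary cost of using ranks.

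**Step 4: simulation with ApoE4 strata.** 4,000 normal-data trials per row, 80 per arm, SD of change 16, difference 7.15. Monte Carlo error is about 0.6 points. The van Elteren column is the Wilcoxon test stratified by ApoE4 only.

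| r | Assumed carrier effect (DMI units) | Wilcoxon | van Elteren | Stratified rank ANCOVA | ANCOVA |
|---|---|---|---|---|---|
| 0.5 | 0 | 77.5% | 77.2% | 87.5% | 89.4% |
| 0.5 | −4 | 78.8% | 78.9% | 88.1% | 90.5% |
| 0.5 | −8 | 79.0% | 80.9% | 90.3% | 92.0% |
| 0.8 | 0 | 78.9% | 78.6% | 82.1% | 84.2% |
| 0.8 | −4 | 78.2% | 78.4% | 82.2% | 84.6% |
| 0.8 | −8 | 79.5% | 80.9% | 84.4% | 87.1% |

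Stratifying by ApoE4 alone gains at most about 2 points, even with an 8-unit carrier effect. In that extreme case the total gap is about 11 points (r = 0.5) and 5 points (r = 0.8). Separate runs with no carrier effect gave gaps of about 8 to 9 points at r = 0.5 and 2 to 3 points at r = 0.8.

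**Step 5: disagreement when the data are normal.** In a further 8,000 trials per setting with no carrier effect, I took the trials in which the parametric ANCOVA was significant. The Wilcoxon test was not significant in 14% of them at r = 0.5 and 9% at r = 0.8. For the stratified rank ANCOVA the figures were 4% and 5%.

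**Step 6: validity.** With no treatment effect, the Wilcoxon test rejected in 4.9% and 5.6% of trials in two settings (Monte Carlo error about 0.3 points). Type I error is nominal.

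**Step 7: the other reading of SD 16.** If 16 is the SD of the score and r = 0.8, the SD of change is 16 × √(2 × 0.2) = 10.1. Power is then 99.2% for Wilcoxon, 99.6% for rank ANCOVA and 99.7% for ANCOVA.

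**The case against.** The strongest reply is that no inference is at risk. Primary conclusions come from the MMRM, tested 25 mg first and then 10 mg (SAP 8.3). No rule makes success depend on the Wilcoxon test or labels a result fragile when that test is not significant. An unadjusted distribution-free test is an ordinary supportive analysis, and its error rate is correct. All of this stands.

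It can also be said that the size depends on a correlation the documents do not give, and that on one reading of SD 16 nothing material is lost. That stands too.

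Several stronger readings are tempting, and the documents do not support them:

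- *The check ignores baseline.* Baseline is subtracted in the change score. Only covariate adjustment is missing.
- *Omitting the ApoE4 strata costs real power.* Stratification alone is worth 0 to 2 points.
- *The plan has no check of normality, or lets a normality test choose the method.* A residual test is planned separately, and no decision rule is attached to it. That test does not, however, show whether the treatment result survives non-normality.
- *The test as described lacks pairwise comparisons.* The text specifies them. Only the illustrative code falls short.

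An adjusted rank test alone would not settle attribution either, since it would still omit pooled site and the earlier visits. The fix therefore needs a matched parametric comparator.

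**Conclusion.** The point holds at low severity. The planned Wilcoxon test is valid, but it is unadjusted and unstratified, and it differs from the MMRM in baseline adjustment, ApoE4, pooled site and use of earlier visits. A discrepancy between the two could not be put down to non-normality alone. That is a matter of design and does not depend on the power figures.

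For a difference of 7.15 and an SD of change of 16, the avoidable loss is about 2 to 4 points at r = 0.8 and about 8 to 10 points at r = 0.5, nearly all from not adjusting for baseline. These figures rest on normal data and an assumed correlation. The loss is negligible if 16 is the score SD and r is 0.8. A reader might infer that the primary result or its error control is compromised. Neither is affected.

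**What to change.** In SAP 8.1.2, for each active-placebo pair:

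1. Restrict the data to the two arms, so that the code yields the pairwise p-values described.
2. Within each ApoE4 stratum, rank Week 13 change and baseline DMI, regress the first on the second, and apply a stratified mean score test (van Elteren weights) to the residuals.
3. Beside it, report a parametric ANCOVA on the same two arms and the same Week 13 observed cases, with the same baseline and ApoE4 adjustment. The two then differ, in essence, only in the distributional assumption. Any gap between this ANCOVA and the MMRM reflects site, earlier visits and the handling of missing data.

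The unadjusted Wilcoxon test may stay as a secondary display. The cost is a few lines of SAP text and code, using data already collected.

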8.2. Secondary Efficacy Endpoints and Analyses

Change from baseline will be evaluated for each of the outcome measures below, using similar MMRM models as used for the primary efficacy endpoint.

This document is confidential.

- RBANS total score, as well as immediate memory, visuospatial/constructional, attention, and language indices
- Alzheimer's Disease Cooperative Study Activities of Daily Living Inventory - Mild Cognitive Impairment version (ADCS-ADL) total score
- Mini-Mental State Evaluation (MMSE) score
- Clinical Dementia Rating sum of boxes (CDR-SB) score
- Modified ADCOMS (m-ADCOMS) Composite Endpoint.

For the analysis of secondary efficacy endpoints, the primary efficacy population will be the mITT population. The PP population and the CP population may be used to evaluate the robustness of the mITT results if the mITT population is materially/substantially greater in sample size (ie, 10% or more) than those two populations. Otherwise, analyses for those two sensitivity populations will not be performed.

An analysis of the Clinical Global Impression- Improvement (CGI-I) score will also be provided.

8.2.1. RBANS total Score and other RBANS index scores

The RBANS total score will be analyzed similarly as for the primary analysis for the primary efficacy endpoint in [Section 8.1](#). The original RBANS total score and change from baseline will be summarized by treatment group at each time point. The LS Mean and SE of change from baseline in RBANS total score over time will also be presented graphically by treatment group.

The pairwise differences in change from baseline between the treatment groups will be assessed at each time point.

Age-based index scores are generated for each RBANS domain as well as a total scale, also expressed as an index score (normal mean=100; SD=15) that ranges from 40-160, calculated from the RBANS stimulus document. Change from baseline in the other RBANS index scores (immediate memory, visuospatial/constructional, attention, language) will be summarized by time point, and analyzed similarly as the primary efficacy endpoint.

8.2.2. ADCS-ADL Total Score

The Alzheimer's Disease Cooperative Study scale for ADL (ADCS-ADL) is administered by an independent rater. The ADCS-ADL is an interviewer-administered informant-based scale where the informant (caregiver) responds to 23 activities of daily living questions about the subject. The questions range from basic to instrumental activities of daily living and take approximately 20 minutes to complete. The total score ranges from 0-78 and a higher score signifies greater functional ability.

Functional ability as assessed in any disease state, including AD, is typically described in terms of activities of daily living (ADLs) that are divided into broad conceptual categories of basic ADLs (BADLs) and instrumental ADLs (IADLs). The ADCS-ADL is a 23 item scale that includes 6 BADL items and 17 IADL items that provide a total score from 0-78, with a lower score indicating greater severity. Caregivers are asked to rate the degree to which their family member or loved one can perform a variety of tasks.

Basic score will also be calculated as the sum of questions 1-6b and ranges from 0-22 (activities included in the basic score are: eating, walking, using the toilet, bathing, grooming and dressing) and Instrumental

This document is confidential.

score, sum of questions 7-23, ranges from 0-56. (activities included in the instrumental score are: using the telephone, watching television, conversations, clearing dishes, personal belongings, making drinks, making snacks, taking rubbish out, getting out and about, shopping, keeping appointments, being left alone, current events, reading, writing, pastimes/hobbies, household chores).

The ADCS-ADL scores (total, as well as basic and instrumental sub-scores) will be analyzed similarly as for the primary analysis for the primary efficacy endpoint in [Section 8.1](#). The ADCS-ADL scores and change from baseline will be summarized by treatment group at each time point. The LS Mean and SE of change from baseline in ADCS-ADL scores over time will also be presented graphically by treatment group.

The pairwise differences in change from baseline between the treatment groups (will be assessed at each time point).

8.2.3. Mini-Mental State Evaluation (MMSE) Score

The Mini-Mental State Examination (MMSE) is a 30-point questionnaire that is used extensively in clinical and research settings to measure cognitive impairment. It is commonly used to screen for dementia. It consists of a series of questions and tests, each of which scores points if answered correctly. The MMSE tests a number of different mental abilities, including a person's memory, attention and language.

The MMSE [[Folstein 1975](#)] consists of 11 items covering orientation, memory (recent and immediate), concentration, language and praxis. Scores range from 0 to 30, with lower scores indicating greater cognitive impairment. Scores for each of the 11 individual tests are not recorded on the CRF, therefore if any item is missing then the total score will be set to missing.

The maximum MMSE score is 30 points, with lower scores indicating worse disease. A score of 20 to 24 suggests mild dementia, 13 to 20 suggests moderate dementia, and less than 12 indicates severe dementia. On average, the MMSE score of a person with Alzheimer's declines about two to four points each year. (source: https://www.alz.org/alzheimers-dementia/diagnosis/medical_tests)

The MMSE scores will be analyzed similarly as for the primary analysis for the primary efficacy endpoint in [Section 8.1](#), using an MMRM. The MMSE scores and change from baseline will be summarized by treatment group at each time point. The LS Mean and SE of change from baseline in MMSE scores over time will also be presented graphically by treatment group.

The pairwise differences in LS Mean change from baseline between the treatment groups will be assessed at each time point.

8.2.4. Clinical Dementia Rating Sum of Boxes (CDR-SB) Score

The Washington University Clinical Dementia Rating scale [[Morris 1993](#)] is a structured, clinician-rated interview that collects information on cognitive capacity from both the collateral source and subject for the evaluation of staging severity of dementia. The CDR was developed primarily to assess severity level in persons with dementia but it can be used to stage dementia in other illnesses as well (eg, Parkinson's disease). Six domains are assessed and then synthesized to assign a Global CDR score. The domains are memory, orientation, judgment and problem solving, community affairs, home and hobbies, and personal care. Impairment is defined only when caused by cognitive loss rather than by physical disability or other non-cognitive factors. Severity ratings range along a 5-point scale (except for the personal care domain):

This document is confidential.

- CDR-0: no cognitive impairment
- CDR-0.5: questionable or very mild dementia
- CDR-1: mild
- CDR-2: moderate
- CDR-3: severe

The CDR is frequently utilized in clinical and research settings to describe stage-dependent features of dementia and for use as a clinically-meaningful outcome measure in clinical drug trials.

CDR is an ordinal parameter (scale 0-3) and is only collected at baseline and Week 13. The CDR sum of boxes (CDR-SB) score is obtained by summing each of the domain box scores, with scores ranging from 0 (least impairment) to 18 (severe impairment).

The CDR-SB score (and each individual domain) will be analyzed similarly as for the primary analysis for the primary efficacy endpoint in [Section 8.1](#). The CDR-SB score and change from baseline will be summarized by treatment group. The LS Mean and SE of change from baseline in CDR-SB scores will also be presented graphically by treatment group.

The pairwise differences in change from baseline between the treatment groups will be assessed at Week 13.

8.2.5. Clinical Global Impression- Improvement (CGI-I) Score

The CGI-I employs a 7-point Likert scale to measure the overall improvement in the subject's condition posttreatment. The Investigator will rate the subject's total improvement whether or not it is due entirely to drug treatment. Response choices include: 0=not assessed, 1=very much improved, 2=much improved, 3=minimally improved, 4=no change, 5=minimally worse, 6=much worse, and 7=very much worse.

The CGI-I does not, by its very definition, have a baseline, and thus the model for this variable will not include a baseline covariate. The CGI-I will be analyzed similarly as for the primary analysis for the primary efficacy endpoint in [Section 8.1](#), with modification to the MMRM model accordingly.

A table of the number (%) of subjects by each CGI-I response category will be provided for each study visit. A CMH row means scores test (stratified by ApoE allele) will be provided at each time point. Further, at each time point, subjects will be dichotomized as 'improved' or 'not improved', and p-values will be derived to test the treatment group comparability accordingly (using a CMH test).

The percentage of subjects with each score at each visit will also be presented graphically by treatment (via bar chart).

An analysis will be performed by using PROC GLIMIX in SAS, and the cumulative odds ratios will be obtained by using the ESTIMATE statement. The difference between treatment groups will be evaluated by a generalized linear model (GLM) at each time point. The model will include fixed effects of ApoE4 stratification factor, study site (pooled), and treatment group. The cumulative odds ratios will be presented along with the SE, a 95% CI, and the p-value.

This document is confidential.

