3.2. Brief Description

This is a Phase 2, randomized, double-blind, placebo-controlled, 3-arm, parallel-design study to evaluate the effects of BPN14770 in approximately 255 subjects with a clinical diagnosis of early stage AD. The study will consist of a Screening period of 28 days or less. The Screening period will be followed by a 13-week double-blind treatment period, and a final follow-up visit for safety one week after treatment is concluded.

Randomization will be stratified based on presence or absence of an ApoE4 allele in the subject's genetic profile. Within each stratum, subjects will be randomized in a blinded, balanced fashion to receive either BPN14770 10mg bid, BPN14770 25 mg bid, or matching placebo. A target of 80 evaluable subjects per group (240 total) is planned (see the sample size determination in [Section 3.4](#)). Approximately 85 subjects per group will be enrolled (255 total) in order to account for potential dropouts. Subjects will have a total of eight clinic visits: Screening; Baseline (Day 1); Weeks 1, 2, 4, 8, 13, and the final Follow-up Visit. The screening visit will consist of consenting the subject, obtaining a medical history, full physical exam, height, weight, BMI, ECG, serology and drug testing, chemistry, hematology, urinalysis, ApoE4 testing, pregnancy testing, and cognitive assessments. If the subject fully qualifies for the study, randomization will occur at the Baseline visit following verification of continued eligibility, at which time the subject will receive study medication.

Cognitive testing will occur at each visit, Week 1 through Week 13, but not at the final Follow-up Visit (note, not all cognitive assessments are performed at each visit). Safety assessments will also be performed at each visit, to include adverse event monitoring, vital signs, ECG, and chemistry and hematology. Urinalysis will also be performed at Screening and Baseline and Weeks 1, 4 and 13. Lipid testing will be performed at Baseline and Week 13. Risk of suicidality will be assessed at Screening, Baseline and Weeks 1, 4, and 13.

Pharmacokinetic sampling will be performed at the clinic visits at Weeks 1, 4, 8 and 13.

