3.5. Treatment Assignment & Blinding

In this randomized, double-blind, placebo controlled, 3-arm, parallel group study, 255 subjects will be assigned to receive one of three treatments via balanced randomization (1:1:1). Randomization will occur separately within each ApoE4 stratum (presence/absence of ApoE4 isoform) to ensure similar numbers of ApoE4 positive subjects are present in each treatment group. The three treatments are:

- A. BPN14770 10mg, twice-daily
- B. BPN14770 25mg, twice-daily
- C. Matched placebo, twice daily

A randomization schedule will be generated by a statistician unassociated with the study execution prior to the start of the study. Subjects will be randomized on Day 1 and receive their bottle of medication that same day.

This is a randomized, double-blind study, meaning that neither site staff nor subject will know what the subject is receiving. Sponsor staff are also blinded to treatment assignments.

Randomization codes will be provided to the Investigator or designee for use in case of an emergency code break requirement. Confirmation of receipt of the randomization code will be required by the Sponsor. The PI or designee will be responsible for maintaining the blind, consistent with protocol design, throughout the study, except in the case of an emergency code break.

The Investigator will be required to notify the Sponsor in the event of any breaking of the blind for any reason. Blinding is not to be broken during the study unless considered necessary by the Investigator for emergency situations for reasons of subject safety. The Investigator should contact the Medical Monitor before breaking the blind. When the blind is broken, the reason must be fully documented.

Except in the event of an emergency code break for an individual subject, the subjects, Investigator, and all other study personnel involved with subject assessments will remain blinded to the actual treatment assignments of the subjects. The Investigator will be ultimately responsible for ensuring that the integrity of the blind is maintained throughout the study.

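### The CGI-I models carry no baseline severity score although MMSE is measured on Day 1; adjusting for it may gain a little precision or power

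*SAP*

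**What the plan says.** SAP 8.2.5 plans several analyses of CGI-I, which the investigator rates at Weeks 1, 2, 4, 8 and 13:

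- An MMRM like the primary one, with one term removed. The SAP argues that CGI-I by definition has no baseline, "and thus the model for this variable will not include a baseline covariate".
- A cumulative-odds model at each time point: "The model will include fixed effects of ApoE4 stratification factor, study site (pooled), and treatment group".
- A CMH row mean scores test stratified by ApoE allele, and a CMH test of improved versus not improved.

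None of these adjusts for baseline severity. The other five secondary endpoints in SAP 4.2 are analysed with models similar to the primary model of SAP 8.1, which includes the baseline score of the scale analysed.

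Pre-dose severity is on record. MMSE is done at Screening (Protocol 10.2) and again on Day 1 before randomization (Protocol 10.3), and a score of at least 20 is required for entry (Protocol 6.2). CDR is done at Screening and Week 13 but not on Day 1. SAP 6.2 defines baseline as the last non-missing value before the first dose, with Screening as the fallback.

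**The concern.** A covariate need not be on the same scale as the outcome. The lack of a CGI-I baseline explains why the usual term drops out, but it gives no reason to leave out MMSE, and the SAP offers no other reason.

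The documents treat baseline MMSE as relevant elsewhere. Protocol 11.4 allows supplemental analyses by it, SAP 6.6 uses it as a subgroup factor for the primary endpoint, and SAP 7.2 tabulates it by arm. SAP 8.2.5 also has the investigator rate total improvement whatever its cause, so the course of the disease enters the rating. A link with baseline severity is plausible, though the documents do not show one.

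Randomization is stratified by ApoE4 only, so MMSE balance is left to chance. SAP 8.3 makes the secondary endpoints part of the evidence for choosing the Phase 3 dose. If MMSE does predict CGI-I, the unadjusted models give up some precision or power on one of those endpoints.

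**Working it through.** **The plan's own figure.** SAP 3.4 gives power for the primary endpoint only: 80% at a two-sided level of 0.05, with 80 per group and a 7.15-unit advantage of 25 mg over placebo on RBANS DMI. It assumes that "the standard deviation of the response variable is 16".

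- Standard error of the difference: 16 × √(2/80) = 2.530.
- Power: Φ(7.15/2.530 − 1.96) = Φ(0.866) = 80.7% by the normal approximation, or 80.2% by the noncentral t.
- Required n: 79 per group. The t-based calculation also reproduces every sample size in Table 1.

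The stated figure holds. No SD, effect size or power is stated for CGI-I.

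**MMRM, taken at one visit.** Let r be the correlation between baseline MMSE and CGI-I (strictly, what remains after ApoE4 and pooled site). Adjustment multiplies the residual variance by 1 − r² and the standard error by √(1 − r²), so 80 per arm is worth 80/(1 − r²). Both r and the standardized CGI-I effect (SMD) are assumptions. Power is Φ(SMD / [√(2/80) × √(1 − r²)] − 1.96).

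| Assumed r | SE multiplier | 80 per arm worth | Power, SMD 0.30 | Power, SMD 0.45 |
|---|---|---|---|---|
| 0 | 1.000 | 80.0 | 47.5% | 81.2% |
| 0.1 | 0.995 | 80.8 | 47.9% | 81.6% |
| 0.2 | 0.980 | 83.3 | 49.1% | 82.8% |
| 0.3 | 0.954 | 87.9 | 51.2% | 84.7% |
| 0.4 | 0.917 | 95.2 | 54.4% | 87.4% |

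One extra degree of freedom among about 240 subjects costs roughly 1/240 of the variance. The break-even is therefore near r = √(1/240) ≈ 0.065.

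**Chance imbalance.** With 80 per arm, the standard error of a standardized MMSE difference between two arms is √(2/80) = 0.158. About 1 comparison in 20 will differ by more than 1.96 × 0.158 = 0.31 SD. At r = 0.3 an imbalance of that size shifts the CGI-I difference by 0.3 × 0.31 ≈ 0.09 SD; at r = 0 it shifts nothing.

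**Cumulative-odds model.** The variance formula above does not carry over, so this model was simulated: two arms of 80, five collapsed categories with assumed shares of 6, 22, 45, 20 and 7%, an assumed marginal log odds ratio near 0.8, 400 runs per setting, and likelihood-ratio tests at 5%. ApoE4 and site were left out. Here r is on the latent scale.

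| Assumed r | Log OR, without → with MMSE | SE | Power |
|---|---|---|---|
| 0.2 | 0.801 → 0.814 | 0.298 → 0.299 | 77.0% → 77.0% |
| 0.3 | 0.799 → 0.846 | 0.298 → 0.300 | 78.2% → 81.5% |
| 0.5 | 0.783 → 0.935 | 0.297 → 0.305 | 76.5% → 87.2% |

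Each simulated power has a Monte Carlo error of about √(0.78 × 0.22/400) ≈ 2 points. The standard error does not fall. Power rises, where it does, because the conditional log odds ratio is larger.

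**The case against.** The SAP makes no error here. CGI-I already rates change, each of the other models adjusts for its own scale's baseline, and the SAP says openly why that term drops out. Omitting a prognostic covariate does not bias a randomized comparison, and the unadjusted standard error already allows for chance imbalance. The study is powered for the primary endpoint only. CGI-I is tested at a nominal level, and only if that dose's primary comparison is significant. Entry limits of MMSE 20–30 and global CDR 0.5 or 1 tend to weaken any correlation, and SAP 7.2 would make an MMSE imbalance visible.

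All of that stands. It limits how much the change is worth, but it identifies no real cost to making it.

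A reader might infer more than the documents support:

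- *Precision is certainly lost.* That requires MMSE to predict CGI-I, and no correlation is given. At r = 0 nothing is lost.
- *The sample-size equivalents apply to both models.* They are linear-model results. In the cumulative-odds model the standard error does not shrink, and the odds ratio changes meaning from marginal to conditional on MMSE.
- *Baseline imbalance passes in full into the CGI-I comparison.* It passes only in proportion to r.
- *CDR-SB would serve equally well.* Its baseline is the Screening value, normally up to 28 days before dosing and possibly longer where washout is needed (Protocol 5.1). MMSE is repeated on Day 1.

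**Conclusion.** The point holds as an inexpensive improvement, not as a defect. SAP 8.2.5 leaves baseline severity out of the CGI-I models for a reason that excludes only a CGI-I baseline, while MMSE should be available before dosing for essentially every randomized subject.

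The size rests on an assumed r. For r of 0.1 to 0.3 the MMRM standard error falls by about 0.5% to 5%, worth roughly 0.4 to 3.7 power points at an assumed SMD of 0.30 to 0.45. The gain becomes material only at about r = 0.4 or more. In the cumulative-odds model the simulated gain was nil at r = 0.2 and about 3 points at r = 0.3, under the assumed category shares and effect. Given the narrow MMSE range, the lower end is more likely. The validity of the randomized comparison is not in question.

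**What to change.** In SAP 8.2.5, replace the sentence excluding a baseline covariate. Before unblinding, prespecify baseline MMSE (Day 1, or Screening if Day 1 is missing, as SAP 6.2 already provides) as a continuous covariate in both the CGI-I MMRM and the cumulative-odds model. State that the reported cumulative odds ratio is then conditional on baseline MMSE. The ApoE-stratified CMH row mean scores test can stay as the supportive analysis without MMSE adjustment, labelled as such.

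The cost is a short SAP edit and about one degree of freedom per model. No new data are needed. Made after unblinding, the same change could look data-driven.
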